5.2.2. Analyses for Continuous Data

Mixed Effect Model Repeat Measurement (MMRM) for Longitudinal Continuous Data:

The fixed effects of treatment, visit, and treatment-by-visit interaction will be included, along with patient as a random effect. Unstructured covariance matrix will be assumed.

When modeling the change from baseline values, the variable of visit will start with the first post-baseline visit, and the actual baseline value will be included as a covariate. At each visit, estimates of mean values and the mean differences between the active treated group and the placebo group will be derived from the model. The corresponding p-values, standard errors and 95% confidence intervals will also be derived from the model.

Below is an example of potential statistical analysis system (SAS) code:

```
PROC MIXED DATA=XXX;  
  CLASS SUBJID TREATMENT VISIT;  
  MODEL CHGBASE=TREATMENT VISIT TREATMENT*VISIT BASE/ALPHA=0.05 DDFM=KR;  
  REPEATED VISIT/SUBJECT=SUBJID TYPE=UN;  
  LSMEANS TREATMENT*VISIT/ALPHA=0.05 CL DIFF;  
RUN;
```

Analysis of Covariance (ANCOVA) for Non-longitudinal Continuous Data:

The non-longitudinal continuous data will be analyzed by ANCOVA with treatment as the factor. When modelling change from baseline values, the actual baseline value will be included as a covariate. Active dose group will be contrasted versus placebo.

Below is an example of potential SAS code:

```
PROC MIXED DATA=XXX;  
  CLASS TREATMENT;  
  MODEL CHGBASE=TREATMENT BASE/ALPHA=0.05;  
  LSMEANS TREATMENT/ALPHA=0.05 CL PDIFF;  
RUN;
```

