6.1.1. Primary Analysis

The primary analysis will be based on the Bayesian analysis outlined in [Appendix 4](#). The Bayesian analysis will be based on ITT population set.

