6.1.2. Sensitivity/Robustness Analyses

There are 3 sets of analyses.

Set 1:

The sensitivity analysis will be based sensitivity prior models on the Bayesian analysis outlined in [Appendix 4](#). The Bayesian analysis will be based on ITT population set.

Set 2:

- Population set
 - ITT;
 - PP.
- Missing data imputation
 - Observed;
 - LOCF.
- ANCOVA (see [Section 5.2.2](#))
 - Baseline SDAI as a covariate;
 - Baseline SDAI and previous anti-TNF use as covariates.

Set 3:

- Population set:
 - ITT;
 - PP.
- Missing data imputation – none (Observed);
- MMRM (see [Section 5.2.2](#)) for analysis of change from baseline in SDAI at Weeks 4, 8, and 12:
 - Baseline SDAI as a covariate;
 - Baseline SDAI and previous anti-TNF use as covariates.

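### The MMRM in SAP 5.2.2 imposes one baseline slope on Weeks 4, 8 and 12, which loses Week 12 precision if that slope differs by visit

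*SAP*

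**What the plan says.** SAP 5.2.2 sets out the model for longitudinal continuous data: "The fixed effects of treatment, visit, and treatment-by-visit interaction will be included, along with patient as a random effect". For change from baseline it adds that "the variable of visit will start with the first post-baseline visit, and the actual baseline value will be included as a covariate". The sample code matches: "MODEL CHGBASE=TREATMENT VISIT TREATMENT*VISIT BASE/ALPHA=0.05 DDFM=KR", with "REPEATED VISIT/SUBJECT=SUBJID TYPE=UN" for the covariance. BASE appears only as a main effect.

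Later sections do not change this. SAP 6.1.2 Set 3 uses the model "for analysis of change from baseline in SDAI at Weeks 4, 8, and 12", in one version with baseline SDAI and in another with previous anti-TNF use added. SAP 6.2, SAP 6.3 and Appendix 1 name MMRM for the continuous secondary and PRO endpoints without further terms.

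The primary analysis (SAP 6.1.1 and Appendix 4) is a separate Bayesian ANCOVA. Set 2 in SAP 6.1.2 is a frequentist ANCOVA. Both fit Week 12 alone, so each estimates its own Week 12 slope.

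**The concern.** The slope of change on baseline at a given visit equals corr(baseline, visit) × SD(visit) / SD(baseline) − 1. A single slope is right only if this quantity is the same at Weeks 4, 8 and 12. Correlation with baseline commonly weakens as time passes, which would steepen the slope. The SAP gives no reason to hold it fixed while letting everything else vary by visit.

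Two things are at stake. The first is precision at Week 12 for the endpoints modelled over the three visits: SDAI, the DAS28 versions, hsCRP, joint counts, PhGA, PAAP, PtGA and HAQ-DI. The second is how Set 2 and Set 3 compare. A difference between them should show the effect of missing-data handling. With a common slope they can differ even when no data are missing.

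**Working it through.** **Inputs from the documents.** Protocol section 3 gives a 6:6:6:5:5:5 allocation and Protocol 9.1 gives 198 completers. 198/33 = 6, so the arms are 6 × 6 = 36 and 6 × 5 = 30, as stated. The enrolment figure also reproduces: 198/0.85 = 233 and 198 × 1.15 = 228, against a stated figure of about 230. SAP 5.2.2 supplies the model, the unstructured covariance and 95% intervals. No precision or power is stated for the MMRM, so there is no MMRM figure to reproduce.

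**Assumed inputs.** The documents give no SDAI SD, slopes or correlations. I took SD 12 at baseline and every visit, and residual correlation ρ^|lag| with ρ = 0.4, 0.6 and 0.8. With equal SDs, slope = correlation with baseline − 1.

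**Formulas.** Let b be the vector of true slopes and S the residual covariance matrix.

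- The common slope converges to β = (1′S⁻¹b) / (1′S⁻¹1).
- The Week 12 contrast variance is multiplied by 1 + (b₁₂ − β)² × Var(baseline) / (Week 12 residual variance).

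**Worked case (moderate growth, ρ = 0.6).** Slopes are −0.30, −0.45 and −0.55, and β = −0.386. The Week 12 residual variance is 144 × (1 − 0.45²) = 114.84. The multiplier is 1 + (0.164)² × 144/114.84 = 1.034, so the standard error rises by 1.7%.

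| Slopes at Weeks 4 / 8 / 12 | Week 12 SE inflation, ρ = 0.4 to 0.8 | Power of a contrast that has 80% with visit-specific slopes (30 vs 36) |
|---|---|---|
| Constant: −0.40 / −0.40 / −0.40 | 0% | 80% |
| Mild: −0.35 / −0.40 / −0.45 | 0.2 to 0.3% | 79.8% |
| Moderate: −0.30 / −0.45 / −0.55 | 1.4 to 2.5% | 78.9 to 78.0% |
| Strong: −0.20 / −0.40 / −0.60 | 4.8 to 9.1% | 76.3 to 72.9% |

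A fivefold steepening (−0.15 / −0.45 / −0.75) would give 12 to 21%. Nothing in the documents points to it and I do not rely on it.

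**Simulation check.** 1,000 trials per scenario, arms of 30/30/36/36/36, ρ = 0.6, REML with unstructured covariance, and dropout completely at random. The table gives the mean model-based Week 12 standard error.

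| Scenario | Common slope | With BASE*VISIT | Week 12 ANCOVA, observed cases |
|---|---|---|---|
| Constant, complete data | 2.369 | 2.371 | 2.371 |
| Moderate, complete data | 2.691 | 2.653 | 2.652 |
| Strong, complete data | 2.879 | 2.725 | 2.724 |
| Constant, about 15% dropout | 2.527 | 2.531 | 2.582 |
| Moderate, about 15% dropout | 2.878 | 2.830 | 2.890 |
| Strong, about 15% dropout | 3.071 | 2.896 | 2.957 |

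- These agree with the formula: about 1.5% and 5.7% inflation with complete data, and 1.7% and 6.1% with dropout.
- The spread of the estimates themselves is noisier over 1,000 trials. It rose by 0.7% and 3.0% with complete data, and by 2.4% and 6.5% with dropout.
- With complete data, BASE*VISIT reproduces the ANCOVA.
- In the strong case with dropout, the common-slope MMRM is less precise than the simple observed-case ANCOVA (3.071 against 2.957).
- If the slope is constant, the extra term costs 2.371/2.369 = 1.001, or 2.531/2.527 = 1.002 with dropout.

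**Baseline imbalance.** One standard error of chance imbalance at baseline is 12 × √(1/30 + 1/36) = 2.97 points. At ρ = 0.6 the common slope leaves 2.97 × (0.55 − 0.386) = 0.5 SDAI points uncorrected (moderate) or 2.97 × (0.60 − 0.282) = 0.9 (strong). This averages to zero over randomisations.

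**The case against.** The strongest case against the point is that little depends on this model. Separation from placebo is judged on the Bayesian posterior (SAP 5.1), futility uses the same framework (SAP 7), and the multiplicity-adjusted pairwise tests in Protocol 9.2 use ANCOVA. Set 2 already supplies a Week 12 ANCOVA with its own slope. All of that stands, and it limits the point to a refinement.

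Growth of the slope is also an assumption. Entry requires joint-count thresholds at both Screening and Baseline, so regression to the mean could already give a substantial slope at Week 4. With a constant slope the loss is zero. That stands too.

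The code is introduced by "Below is an example of potential statistical analysis system (SAS) code", so one might say it does not bind. This does not remove the point, because the text lists the same terms.

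A reader might infer more than the documents support:

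- **That the common slope fits no visit well.** Under moderate growth the inflation is at most 1.0% at Week 4, 0.7% at Week 8 and 2.5% at Week 12.
- **That treatment effects are biased.** Randomisation rules out systematic bias; the issue is precision.
- **That Set 3 is the only robustness check.** It is one of three sets.
- **That every PRO endpoint is affected.** SF-36, EQ-5D-3L and FACIT-F are analysed at Week 12 only, where common and visit-specific slopes are the same model.
- **That the extra term reduces bias from missing data.** The simulated dropout was completely at random, so this was not tested.

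**Conclusion.** The point holds as a question of efficiency. SAP 5.2.2 fixes one baseline slope in both text and code, and no later section relaxes it. The Week 12 cost in standard error is 0% if the slope is constant, 0.2 to 0.3% under mild growth, 1.4 to 2.5% under moderate growth and about 5 to 9% only under strong growth.

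These figures rest on the assumed SD of 12, the residual correlations and the slope patterns, so the documents do not settle which row applies. Validity is not in question and no stated decision rule changes. The case for acting is the asymmetry: the term costs almost nothing if it is not needed and recovers precision if it is.

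**What to change.** Add baseline-by-visit to the list of fixed effects in the SAP 5.2.2 text, and BASE*VISIT to the MODEL statement. With complete data the Week 12 contrasts then equal those of the Week 12 ANCOVA with the same population and covariates. Differences between Set 2 and Set 3 would then reflect missing-data handling only.

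Optionally, add previous anti-TNF use by visit to the second Set 3 model, so that the same equality holds with its Set 2 counterpart. That addition was not simulated.

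The cost is two degrees of freedom per covariate (three visits, so two extra slopes) and about 0.1% in standard error if the slope is constant. Data collection and the primary analysis are unchanged.

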5.2.3. Analyses for Categorical Data

The frequency and percentage for each category will be presented.

5.2.4. Analyses for Time to Event Data

None.

5.3. Methods to Manage Missing Data

In general, for descriptive statistics missing values will not be imputed. In addition, for safety endpoints missing values will not be imputed. Unless there is an explicit instruction, missing values will be used for lower limits of detection and quantitation.

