7.1.5.2. ACR Responder Analysis

The American College of Rheumatology's definition for calculating improvement in RA (ACR20) is calculated as a 20% improvement in tender and swollen joint counts and 20% improvement in 3 of the 5 remaining ACR-core set measures: patient and physician global assessments, pain, disability, and an acute-phase reactant which for this study will be CRP. Similarly, ACR50 and ACR70 are calculated with the respective percent improvement. Components of the ACR Responder Index will be collected as indicated in the [Schedule of Activities](#).

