9.1. Sample Size Determination

The primary endpoint of the study will be the change from baseline in the simplified disease activity index (SDAI) at 12 weeks. The study will enroll approximately 198 completers allocated as follows:

PF-06650833 400 mg	PF-06650833 200 mg	PF-06650833 60 mg	PF-06650833 20 mg	Tofacitinib 5 mg BID	Placebo
36	36	36	30	30	30

Assuming a 15% dropout rate the study will enroll approximately 230 subjects. Since the use of tofacitinib in this study may be not be acceptable by regulatory authorities/ethics committess in all countries, achieving full randomization into the tofacitinib arm may prove logistically challenging. Since the tofacitinib arm is serving as an active control for the study, enrollment of approximately 20-30 subjects into that arm will be acceptable.

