5.3.1. Binary Endpoint

For the binary response endpoints (eg, SDAI remission rates), subjects with missing values will be handled by:

- non-responder imputation (NRI) method, ie, setting any missing values to be non-responsive (0).
- will be used as observed (ie, excluding any missing values from analysis).

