6.2.2. DAS

For DAS28-3 (ESR), DAS28-3 (CRP), DAS28 -4 (ESR), and DAS28-4 (CRP), analysis of number of subjects with DAS28 remission (DAS <2.6) and DAS28 low disease activity (DAS28 <3.2) at Weeks 4, 8, and 12:

- ITT population set;
- Missing data imputation:
 - Observed;
 - NRI.
- Normal approximation.

Analysis of change from baseline in DAS28-3 (ESR), DAS28-3 (CRP), DAS28 -4 (ESR), and DAS28-4 (CRP) at Weeks 4, 8, and 12:

- ITT population set;
- Missing data imputation – none (Observed);
- MMRM.

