Appendix 3: Data Derivation Details

A patient is said to have achieved the ACR20 criteria⁺ when all of the following bulleted points are true:

- A 20% improvement from baseline in the tender/painful joint count (TCJ28).
- A 20% improvement from baseline in the swollen joint count (SJC28).
- A 20% improvement from baseline in *at least 3* of the following 5 variables:
 1. PhGA of Arthritis VAS;
 2. PAAP VAS;
 3. PtGA of Arthritis VAS;
 4. HAQ disability index;
 5. Results of ESR or CRP blood test (both of which test for inflammation).

ACR50 and ACR70 are defined analogously.

There are many forms of the DAS. The DAS used in this study is the DAS using the 28-count subsets of tender/painful joints and swollen joints, together with either CRP or ESR, to derive the DAS28-3 (CRP), DAS28-4 (CRP), or DAS28-3 (ESR) and DAS28-4 (ESR), which are calculated using the following formulae, respectively:

$$\text{DAS28-4(ESR)} = (0.56 * \sqrt{\text{TJC28}}) + 0.28 * \sqrt{\text{SJC28}} + 0.70 * \ln(\text{ESR}) + 0.014 * \text{GH}$$

$$\text{DAS28-3(ESR)} = [0.56 * \sqrt{\text{TJC28}} + 0.28 * \sqrt{\text{SJC28}} + 0.70 * \ln(\text{ESR})] * 1.08 + 0.16$$

$$\text{DAS28-4(CRP)} = 0.56 * \sqrt{\text{TJC28}} + 0.28 * \sqrt{\text{SJC28}} + 0.36 * \ln(\text{CRP}+1) + 0.014 * \text{GH} + 0.96$$

$$\text{DAS28-3(CRP)} = [0.56 * \sqrt{\text{TJC28}} + 0.28 * \sqrt{\text{SJC28}} + 0.36 * \ln(\text{CRP}+1)] * 1.10 + 1.15$$

where TJC28 is number of painful joints out of 28 joints, SJC28 is number of swollen joints out of 28 joints, GH is the general health or patients' global assessment of disease activity on a 100 mm VAS, ln is the natural logarithm, ESR is in mm/first hour, and CRP is in mg/L.

Handling Missing Joint Counts:

- A missing painful/tender assessment or one NOT DONE at *baseline* is set to “not painful/tender”;
- A missing swollen assessment or one NOT DONE at *baseline* is set to “not swollen”;
- A missing painful/tender assessment or one NOT DONE *post baseline* is set to “painful/tender”;

- A missing swollen assessment or one NOT DONE at *post baseline* is set to “swollen”.

Note that joints marked NOT APPLICABLE are not to be counted in the summation of swollen and painful/tender joints at baseline and post baseline.

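### SAP 5.3 makes below-limit results missing by default with no visible exception for hsCRP, so a very low hsCRP could make DAS28(CRP) uncomputable and exclude a responder or score them as a failure

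*SAP*

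**What the plan says.** - **Default rule.** SAP 5.3, the general section on missing data, says: "Unless there is an explicit instruction, missing values will be used for lower limits of detection and quantitation". The only component-level rules visible in the SAP are those for joint counts in Appendix 3; none covers CRP.
- **Scores that need CRP.** SAP Appendix 3 derives DAS28-3(CRP) and DAS28-4(CRP) with the term 0.36 × ln(CRP+1), and fixes the units: "ln is the natural logarithm, ESR is in mm/first hour, and CRP is in mg/L". Protocol Appendix 7 lists hsCRP among the four components of DAS28-4(CRP).
- **Binary analyses.** SAP 6.2.2 plans, for all four DAS28 scores, the "analysis of number of subjects with DAS28 remission (DAS <2.6) and DAS28 low disease activity (DAS28 <3.2) at Weeks 4, 8, and 12", under both missing-data approaches of SAP 5.3.1. Under NRI this means "setting any missing values to be non-responsive (0"; under the other, missing data "will be used as observed (ie, excluding any missing values from analysis".
- **ACR.** Protocol 7.1.5.2 specifies "an acute-phase reactant which for this study will be CRP". SAP Appendix 3 lists the same item as "Results of ESR or CRP blood test (both of which test for inflammation".

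**The concern.** A result below the assay limit is not an unknown value. It is known to be low, and a low hsCRP is favourable. If it is coded as missing, a good result can leave the numerator of a response rate (Observed) or be counted as non-response (NRI). If this happens, it happens more often in an arm that lowers hsCRP more, so any bias runs against that arm.

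The formula is not the obstacle, because ln(CRP+1) is defined at CRP = 0. Only the missing-value rule blocks the score. At stake are the CRP-based DAS28 remission and low disease activity rates at Weeks 4, 8 and 12 and, under one of two conflicting definitions, one item of the ACR response.

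**Working it through.** No figure in the plan depends on this rule, so there is none to reproduce. The check follows hsCRP through the derivations.

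**Inputs.** Formulas: SAP Appendix 3. Cut-offs 2.6 and 3.2: SAP 6.2.2. Completers per arm, 36 (400, 200 and 60 mg) and 30 (20 mg and placebo): Protocol 9.1, which plans 198 completers from about 230 enrolled. The assay limit L is not in the documents; I assume 0.2 to 1.0 mg/L.

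**1. The chain.** Below-limit hsCRP → missing (SAP 5.3) → DAS28(CRP) missing (inferred, since no component rule exists) → excluded or failure (SAP 5.3.1 and 6.2.2).

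**2. How much of the score is unknown.** CRP lies between 0 and L.
- DAS28-4(CRP): 0.36 × ln(1+L) = 0.066 at L = 0.2 and 0.250 at L = 1.0.
- DAS28-3(CRP): 1.10 times that = 0.072 and 0.274.
- Largest error of half-limit substitution: 0.36 × ln(1+L/2) = 0.034 and 0.146 for DAS28-4(CRP); × 1.10 = 0.038 and 0.161 for DAS28-3(CRP).
- A coarser assay leaves more unknown: at L = 5 mg/L the DAS28-4(CRP) span is 0.645.

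**3. Two worked subjects, both with TJC28 = 1 and SJC28 = 1.** DAS28-4(CRP) = 0.56 + 0.28 + 0.014 × PtGA + 0.96 + 0.36 × ln(CRP+1).

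| PtGA | CRP 0 | CRP 0.2 | CRP 1.0 | Remission (<2.6)? |
|---|---|---|---|---|
| 20 mm | 2.08 | 2.15 | 2.33 | Yes at every value |
| 45 mm | 2.43 | 2.50 | 2.68 | Depends on the value |

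DAS28-3(CRP) does not use PtGA. For both subjects it is (0.84 + 0, 0.066 or 0.250) × 1.10 + 1.15 = 2.07, 2.15 or 2.35, always below 2.6. On DAS28-4(CRP) the second subject crosses 2.6 where 0.36 × ln(1+CRP) = 0.17, that is at CRP ≈ 0.60 mg/L. Remission is thus certain with a limit of 0.2 and uncertain with a limit of 1.0. Both subjects are below 3.2 throughout, so low disease activity is certain. Under NRI both would count as failures on both criteria.

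**4. Cost per lost responder under NRI.** 1/36 = 2.8 points and 1/30 = 3.3 points. With all randomized subjects (factor 230/198) the arms are about 41.8 and 34.8, giving 2.4 and 2.9 points.

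**5. Illustration with assumed counts.** Take 12/36 active and 4/30 placebo responders, a difference of 20.0 points with Z = 2.00 by SAP 5.2.1. If one active responder is below the limit:
- NRI: 11/36 against 4/30, 17.2 points, Z = 1.74.
- Observed: 11/35 against 4/30, 18.1 points, Z = 1.81.

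Both analyses shrink the effect, so one does not correct the other. The counts show scale only and predict nothing.

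**6. ACR.** Three of five items must improve. Where CRP has improved, two of the other four suffice. If CRP is missing and is the only admissible reactant, three of those four are needed. A fall from 7 mg/L (the screening threshold in Protocol 4.1; subjects may instead enter on ESR) to below 0.2 or 1.0 mg/L is an improvement of at least (7 − 0.2)/7 = 97.1% or (7 − 1.0)/7 = 85.7%, enough for that item at the 20%, 50% and 70% levels.

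**The case against.** **Frequency.** The strongest objection is that no case is shown to occur. The assay is high-sensitivity and run centrally, and subjects enter with active disease. The 2.4 to 3.3 points are the cost of one case, not evidence of any. This stands: the total effect is unknown and may be near zero.

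**Reading of the rule.** The sentence is loosely worded and closes a paragraph that otherwise concerns descriptive statistics and safety data. An explicit instruction could sit in redacted SAP text or in sponsor standards. This also stands in part. However, the section governs efficacy endpoints through 5.3.1 and 5.3.2, the sentence is not limited to safety, and the visible references to sponsor standards concern safety and disposition reporting.

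**Mitigation.** DAS28-3(ESR) and DAS28-4(ESR) remission and low disease activity are analysed at the same visits and do not use CRP. They are unaffected and offer a cross-check, but they do not repair the CRP-based results.

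**Stronger readings a reader might infer.**
- That the primary endpoint is compromised. The documents do not support this. Protocol 9.2 carries forward the most recent value of a missing SDAI domain while a subject is enrolled, and the below-limit hsCRP itself is worth only L/10 = 0.02 to 0.10 SDAI points. The decision rule in SAP 5.1 uses the SDAI posterior.
- That most affected subjects are certain remitters. The PtGA 45 mm case shows that status can depend on the value.
- That ACR rates are generally biased. SAP Appendix 3 lets ESR fill the item. The loss arises only under the protocol's CRP-only wording, and only when CRP is the deciding third item.

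**Conclusion.** The point holds as a minor defect in the handling of secondary endpoints. The stated default, with no visible exception, can exclude a subject with a very low hsCRP or score that subject as a failure on CRP-based DAS28 remission and low disease activity, even where the remaining components settle the status.

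This rests on the plain reading of SAP 5.3, on the inference that a missing CRP makes the score missing, and on an assumed limit of 0.2 to 1.0 mg/L for the spans. The loss is about 2.4 to 3.3 percentage points of an arm's rate per misclassified responder. The number of such subjects cannot be derived from the documents. Any bias would run against the arm that lowers hsCRP more.

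The mismatch over the ACR reactant is a separate inconsistency that needs reconciling whatever the assay limit.

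**What to change.** Add to SAP 5.3 or Appendix 3: hsCRP results below the limit of detection or quantitation are not treated as missing; wherever hsCRP enters a derived score they are set to one pre-specified value (for example half the limit), and 0 and the limit are used as sensitivity checks. State the assay limit.

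Half the limit is one convention among several. What matters is that the value is fixed in advance. The sensitivity checks are needed because the choice can move a subject near a cut-off: in the PtGA 45 mm case with L = 1.0, DAS28-4(CRP) is 2.43 at 0, 2.58 at half the limit (2.43 + 0.146) and 2.68 at the limit. If an instruction for hsCRP already exists elsewhere, citing it in SAP 5.3 closes this part.

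Separately, name the same ACR acute-phase reactant in Protocol 7.1.5.2 and SAP Appendix 3.

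The cost is one SAP sentence, one line of derivation code and one wording correction, made before unblinding. No new data are needed.
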